Apremilast in Combination with Clobetasol Spray for the Treatment of Plaque Psoriasis

INVESTIGATIONAL PRODUCT (IP): Apremilast and Clobetasol 0.05% spray

PROTOCOL NUMBER:

DATE FINAL:

EudraCT NUMBER:

IND NUMBER:

SPONSOR NAME / ADDRESS: [name] / [name]

MEDICAL MONITOR / EMERGENCY CONTACT INFORMATION

Name:	[name]
Title:	Principal Investigator/Sponsor Investigator
Address:	[name]
[contact]
E-mail:	[contact]

PROTOCOL SUMMARY

Study Title - Apremilast in Combination with Clobetasol spray for the treatment of plaque psoriasis of the body with or without scalp involvement

Indication – Apremilast is indicated for the treatment of patients with moderate to severe plaque psoriasis who are candidates for phototherapy or systemic therapy

Objectives

Primary Objective – Assessing the efficacy of combining Clobetasol spray with apremilast for the treatment of plaque psoriasis of the body with or without scalp

Secondary Objectives – Assessing the safety and quality of life in patients treated with Clobetasol spray and apremilast for the treatment of plaque psoriasis of the body with or without scalp

Study Design

Study Population- Adults 18 years and older with plaque psoriasis with at least 10% BSA involving the body with or without scalp lesions

Length of Study – 16 weeks

Study Treatments – Clobetasol is a superpotent topical corticosteroid. Many patients who use this may develop a rebound if stopped suddenly¹. Therefore, in this study the drug will be slowly tapered over 6 weeks. Patients with plaque psoriasis on the body with or without scalp involvement (not solely face/folds/hands/feet) begin apremilast at the approved psoriasis dosage. Patients will also begin clobetasol spray 0.05% to affected plaques bid for 2 weeks, then qday for 2 weeks then qod for 2 weeks then stop clobetasol but continue apremilast for a total of 16 weeks.

Overview of Efficacy Assessments – Patients will have BSA x PGA and PASI 75 scores measured at baseline then at 2, 4, 6, 8, 12 and 16 weeks. We will also record pruritus VAS and TSQM version II at all visits. If scalp involvement, we will also report scalp PGA

Primary Clinical Assessment- Proportion of patients achieving PASI 75 at Week 16 from baseline

Additional Clinical Assessments – Adverse Events (AE), Scalp PGA, Pruritus VAS, TSQM version II. Clinical Benefit, mean percent change from baseline in BSA x PGA at Week 16

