1. INTRODUCTION

Approximately 30% of patients with psoriasis vulgaris achieve PASI 75 reduction at 16 weeks with oral apremilast. In a study using clobetasol spray as monotherapy twice daily for 4 weeks, 35.7% achieved clearance and 37.3% were almost clear. Potent topical steroids have the potential for adrenal suppression and skin atrophy with long-term use. For these reasons, they are ideal for inducing remission but not long-term use². The combination of clobetasol spray to induce rapid response with apremilast as a long-term treatment to maintain response may be a good treatment regimen.

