2. STUDY OBJECTIVES

2.1. Primary Objective

Proportion of patients achieving PASI (Psoriasis area and Severity Index) 75 at Week 16 from baseline.

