9.2. Sample Size

The proposed sample size is based on clinical setting, practice size, number of patients able to be included within the 1-year time period. Approximately 20 patients will be enrolled into the study.

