9.5. Efficacy Evaluation

Efficacy analysis will be based on all patients enrolled as specified in the protocol. Responders are those who achieve at least a PASI-75 at Week 16; non-responders are defined as those who do not achieve a PASI-75 at Week 16 and/or those who have missing data at any time point during the study.

The proportion of patients who achieve at least a PASI-75 at Week 16 (responders) reference to the baseline, proportion of patients with scalp psoriasis with improvement of ScPGA scores to 0 and 1 at Week 16, change from baseline in Pruritus VAS at Week 16, mean percent change from baseline in BSA x PGA at Week 16 will be summarized using descriptive summary statistics for continuous variables, while frequency and percentages will be provided for discrete variables

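### Section 9.5 counts an observed Week 16 PASI-75 response as a failure if earlier data are missing, so the primary proportion can only stay the same or fall

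*Combined protocol and SAP*

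**What the plan says.** Section 2.1 gives the primary objective as "Proportion of patients achieving PASI (Psoriasis area and Severity Index) 75 at Week 16 from baseline". The Protocol Summary names the same primary assessment. Neither places any condition on visits in between.

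Section 9.5 begins in agreement: "Responders are those who achieve at least a PASI-75 at Week 16". It then says "non-responders are defined as those who do not achieve a PASI-75 at Week 16" and continues "and/or those who have missing data at any time point during the study". The denominator is fixed in the same section: "Efficacy analysis will be based on all patients enrolled as specified in the protocol".

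On the schedule, the Protocol Summary states: "Patients will have BSA x PGA and PASI 75 scores measured at baseline then at 2, 4, 6, 8, 12 and 16 weeks". That puts five PASI assessments (Weeks 2, 4, 6, 8 and 12) between the two values that define the endpoint. The Table of Events in section 4 also lists BSA x PGA, pruritus VAS, scalp PGA and TSQM at every visit. Section 9.2 gives the size: "Approximately 20 patients will be enrolled into the study". No other section limits the missing-data clause to Week 16 or to PASI, or gives a different missing-data rule.

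**The concern.** Counting a patient with no Week 16 PASI as a non-responder is a common and defensible way to handle an unknown outcome. The clause in 9.5 goes further. A patient seen at baseline and Week 16, with both scores recorded and a PASI-75 response between them, becomes a failure because of, say, a missed Week 4 visit. A known success is replaced by its opposite.

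The quantity reported is then no longer the one in section 2.1. It is the proportion with PASI-75 at Week 16 **and** no missing data, which mixes attendance with efficacy. Such a patient also satisfies the responder sentence in 9.5, so the two categories overlap and the text does not say which prevails. In an open-label study of this size, that leaves a classification of the primary endpoint to be settled after the data are seen.

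The proportion is the trial's main result, and the protocol's only context for it is the response to apremilast alone: "Approximately 30% of patients with psoriasis vulgaris achieve PASI 75 reduction at 16 weeks with oral apremilast". Section 1.2 gives 33.1% and 28.8% from two phase 3 trials. A combination rate lowered by missed interim visits would blur the comparison that the rationale invites.

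**Working it through.** The plan has no figure to reproduce: the sample size rests on feasibility, and no power, target rate or missing-data rate is given.

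**Step 1: which patients the clause affects**

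| Week 16 PASI | Gap elsewhere | Section 2.1 (missing Week 16 = failure) | Section 9.5 with the clause applied |
|---|---|---|---|
| PASI-75 achieved | No | Responder | Responder |
| PASI-75 achieved | Yes | Responder | **Non-responder** |
| Not achieved | Either | Non-responder | Non-responder |
| Missing | Either | Non-responder | Non-responder |

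Only the second row differs.

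**Step 2: direction**

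Let N be the number enrolled, *a* the Week 16 responders with complete data, *b* the Week 16 responders with a gap, *c* the complete non-responders, and *m* those with Week 16 missing.

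- Section 9.5 with the clause: a/N.
- Week 16 rule, all enrolled: (a + b)/N. This is at least a/N because b ≥ 0.
- Week 16 observed cases: (a + b)/(N − m), at least a/N.
- Complete cases: a/(a + c), at least a/N because a + c ≤ N.

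The 9.5 proportion is never above any of these.

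**Step 3: size that follows from the documents**

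With N = 20, each patient in group *b* costs 1/20 = 5 percentage points. For example, if 8 of 20 reach PASI-75 at Week 16 and 2 of the 8 have an earlier gap, the Week 16 rule gives 8/20 = 40% and the clause gives 6/20 = 30%.

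**Step 4: illustration under assumed missing rates**

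Assumptions, none from the documents: each of the five interim visits is missed with the same probability q, gaps are unrelated to response, and baseline and Week 16 PASI are observed. Then

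reported rate = p × (1 − P(any gap)),

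where p is the true Week 16 rate. With independent visits, P(any gap) = 1 − (1 − q)^5. For any dependence between visits, P(any gap) lies between q (all gaps in the same patients) and 5q (no patient has more than one gap).

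| q | P(any gap), independent | p = 30%: independent | p = 30%: limits | p = 50%: independent | p = 50%: limits |
|---|---|---|---|---|---|
| 2% | 9.6% | 27.1% | 29.4% to 27.0% | 45.2% | 49.0% to 45.0% |
| 5% | 22.6% | 23.2% | 28.5% to 22.5% | 38.7% | 47.5% to 37.5% |
| 10% | 41.0% | 17.7% | 27.0% to 15.0% | 29.5% | 45.0% to 25.0% |

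The 30% is the protocol's approximate figure for apremilast alone; the 50% is an assumption. Among 6 true responders (30% of 20), the expected number reclassified with independent gaps is 6 × P(any gap) = 0.58, 1.36 and 2.46.

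**Step 5: scale**

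The exact (Clopper-Pearson) 95% interval for 6/20 is 11.9% to 54.3%. Losing one or two responders (5/20 = 25%, 4/20 = 20%) stays inside it.

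**The case against.** The strongest objection is that 9.5 is ambiguous rather than wrong. Its responder sentence has no completeness condition, and its second paragraph describes the statistic to be summarised as section 2.1 does. A departure from 2.1 follows only if the missing-data clause prevails. It is true that no precedence is stated. But if the responder sentence prevailed, the reference to every time point would change nobody's classification, so reading the clause as an override is the more natural course. On either reading the sentence needs correction.

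The rule is also prespecified, conservative and keeps everyone in the denominator. Study drug is dispensed and counted at treatment visits, so a missed visit might signal a gap in treatment. The documents do not offer that as the reason, and a missed assessment is a poor measure of adherence when tablet counts are planned.

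The illustration rests on chosen missing rates, and the lowest values need half of all patients each to miss one interim visit. That stands: only the direction and the 5-point step come from the documents. The illustration also covers only missed interim visits. The clause is not restricted to PASI, so read literally a blank VAS or TSQM form could trigger it. This widens the problem.

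Finally, there is no test, threshold or control arm, and a shift of one or two patients lies within sampling uncertainty. That limits the severity. It does not justify an avoidable error that always runs in one direction.

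**Conclusion.** The concern holds. Applied as written, the missing-data clause in 9.5 misclassifies patients observed to have met the primary endpoint, and the reported proportion matches section 2.1 only if no Week 16 responder has a gap. Otherwise it is lower by 5 percentage points per affected patient, taking 20 enrolled. This assumes that the clause overrides the responder sentence, which is the natural reading but is not stated.

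The average size in practice cannot be derived from the documents, because it depends on a missing-data rate that they do not give. The error cannot inflate efficacy, and no significance level or power figure is affected. It should be fixed because it concerns the main result, but it is not a fatal flaw.

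**What to change.** Replace the responder and non-responder definitions in 9.5 with two mutually exclusive categories, for example:

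> A responder is a patient with observed baseline and Week 16 PASI whose score has fallen by at least 75%. Every other enrolled patient is a non-responder, including any patient whose baseline or Week 16 PASI is missing for whatever reason. Gaps at other visits, or in other instruments, do not affect this classification.

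Keep all enrolled patients as the denominator. If the stricter count is of interest, report it beside the main result as a sensitivity analysis, stating which data items count as missing. The cost is one or two sentences in 9.5; no visit, assessment or data item is added.

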10. ADVERSE EVENTS

10.1. Monitoring, Recording and Reporting of Adverse Events

An adverse event (AE) is any noxious, unintended, or untoward medical occurrence that may appear or worsen in a subject during the course of a study. It may be a new intercurrent illness, a worsening concomitant illness, an injury, or any concomitant impairment of the subject's health, including laboratory test values (as specified by the criteria below), regardless of etiology. Any

worsening (i.e., any clinically significant adverse change in the frequency or intensity of a pre-existing condition) should be considered an AE. A diagnosis or syndrome should be recorded on the AE page of the CRF rather than the individual signs or symptoms of the diagnosis or syndrome.

All AEs will be recorded by the Sponsor Investigator(s) from the time of signing the informed consent through the end of the designated follow-up period.

All subjects will be monitored for AEs during the study. Assessments may include monitoring of any or all of the following parameters: the subject's clinical symptoms, laboratory, pathological, radiological or surgical findings, physical examination findings, or other appropriate tests and procedures.

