3. OVERALL STUDY DESIGN

Open label, pilot trial with 20 patients with psoriasis vulgaris involving the body with or without scalp plaques

The study is designed as a 16-week study and consists of 8 visits as described in the table of events.

Screening

To reduce risk of gastrointestinal symptoms, titrate to recommended dose of 30 mg BID according to the following schedule:

- Day 1: 10 mg in morning
- Day 2: 10 mg in morning and 10 mg in evening
- Day 3: 10 mg in morning and 20 mg in evening
- Day 4: 20 mg in morning and 20 mg in evening
- Day 5: 20 mg in morning and 30 mg in evening
- Day 6 and thereafter: 30 mg twice daily

Weeks 0-2

Patients will receive apremilast 30 mg BID and clobetasol spray 0.05% to affected plaques BID for 2 weeks. The first week of IP dosing will consist of apremilast dose-titration card.

Weeks 2-4

Patients will receive apremilast 30 mg BID and clobetasol spray 0.05% to affected plaques once daily for 2 weeks

Weeks 4-6

Patients will receive apremilast 30 mg BID and clobetasol spray 0.05% to affected plaques every other day for 2 weeks, then stop clobetasol spray 0.05%

Weeks 6-16

Patients will continue to receive apremilast 30 mg BID

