3.2. Study Duration- 16 weeks

4. TABLE OF EVENTS

Visit	Screening	Baseline	Apremilast Treatment					
	1	2	3	4	5	6	7	8
Week	Up to 7 days	0	2	4	6	8	12	16
Informed Consent	x							
Inclusion/Exclusion Criteria	x	x						
Medical and Disease History	x							
Height	x							x
Weight	x							x
Sex	x							
Race	x							
Prior/Concurrent Medications/Therapies	x	x	x	x	x ^a	x	x	x
Safety Assessments								
Pregnancy Test and Contraception Education for Females of Child- bearing Potential (FCBP)	x	x						x
Psoriasis Flare or Rebound Assessment	x	x	x	x	x	x	x	x
Adverse Events	x	x	x	x	x	x	x	x
Clinical Efficacy Assessments								
BSAxPGA	x	x	x	x	x	x	x	x
PASI	x	x	x	x	x	x	x	x
Pruritus VAS	x	x	x	x	x	x	x	x
Scalp PGA	x	x	x	x	x	x	x	x
TSQM version II	x	x	x	x	x	x	x	x
Investigational Product Dosing								
Dispense IP		x	x	x	x	x	x	x
Return IP tablets, Count for Compliance			x	x	x	x	x	x

^a Discontinue clobetasol spray 0.05% at Week 6

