5. PROCEDURES

The following procedures will be conducted as outlined in the Table of Events.

Informed Consent

An Informed Consent Document will be signed by the subject before any study-related assessments are performed.

Contraception Education

The risks to a fetus or to a nursing child from apremilast are not known at this time. Results of the animal and in vitro studies can be found in the IB.

All females of childbearing potential (FCBP) must use one of the approved contraceptive options as described in section 4.2 while on investigational product and for at least 28 days after administration of the last dose of the investigational product.

When a female subject of childbearing potential's contraceptive measures or ability to become pregnant changes at the time of study entry or at any time during the study, the Sponsor Investigator will educate the subject regarding options and correct and consistent use of effective contraceptive methods in order to successfully prevent pregnancy.

Inclusion/Exclusion Criteria

Subjects must meet all inclusion criteria and must not have any of the conditions specified in the exclusion criteria to qualify for participation in the study. The subject's source documents must support his/her qualifications for the study (e.g., if a female subject does not require pregnancy testing and birth control because of a hysterectomy, the date of the hysterectomy must be included in the medical history).

Medical and Disease History

Relevant medical history should be recorded, including smoking and alcohol history, as well as previous relevant surgeries. Disease history includes history of psoriasis, psoriatic arthritis and chronic infections.

Prior/Concurrent Medications and Therapies

All medications and therapies being taken/used by the subject at the time of consent or at any time during the study will be recorded. Other key medications and therapies will be recorded.

Safety Assessments

The following assessments will be conducted as outlined in the Table of Events.

Psoriasis Flare and Rebound Assessments

Psoriasis flare is an AE (and will be recorded as an AE) and represents an atypical or unusual worsening of disease during treatment. It is defined as a sudden intensification of psoriasis requiring medical intervention or a diagnosis of new generalized erythrodermic, inflammatory, or pustular psoriasis. A more typical, gradual worsening of plaque psoriasis would not be recorded as an AE.⁵

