Rebound is an AE and is defined as a severe and sudden worsening of disease that occurs after treatment has been discontinued. This exacerbation is characterized by a PASI \geq 125% of baseline or a new generalized pustular, erythrodermic or more inflammatory psoriasis after stopping therapy⁶.

Adverse Events

Details of AE reporting may be found in Section 10.

Clinical Efficacy Assessments

The following assessments will be conducted as outlined in the Table of Events, **Table 1**.

Psoriasis Area Severity Index (PASI)

PASI will be determined for all subjects throughout the study.

The PASI is a measure of psoriatic disease severity taking into account qualitative lesion characteristics (erythema, thickness, and scaling) and degree of skin surface area involvement on defined anatomical regions. The PASI is a validated instrument that has become standard in clinical trials for psoriasis.

Psoriasis Area Severity Index scores range from 0 to 72, with higher scores reflecting greater disease severity.⁷ Erythema, thickness, and scaling are scored on a scale of 0 (none) to 4 (very severe) on 4 anatomic regions of the body: head, trunk, upper limbs, and lower limbs. Degree of involvement on each of the 4 anatomic regions is scored on a scale of 0 (no involvement) to 6 (90% to 100% involvement). The total qualitative score (sum of erythema, thickness, and scaling scores) is multiplied by the degree of involvement for each anatomic region and then multiplied by a constant. These values for each anatomic region are summed to yield the PASI score.

Body Surface Area (BSA) x Physician Global Assessment (PGA)

BSA is determined by calculating the number of palms of psoriasis on the scalp and body. One palm of psoriasis represents 1% BSA. PGA is a 5-point scale from 0 (clear) to 4 (severe).

Scalp Physician Global Assessment (ScPGA)

ScPGA will assess scalp involvement, if present at baseline. ScPGA is a 6-point scale from 0 (clear) to 5 (very severe).

Visual Analog Scale (VAS) Assessments

The following assessments will be conducted as outlined in the Table of Events.

Pruritus Visual Analog Scale (VAS) Assessment

The subject will be asked to place a vertical stroke on a 100 mm VAS on which the left-hand boundary represents no itch, and the right-hand boundary represents itch as severe as can be imagined. The distance from the mark to the left-hand boundary will be recorded.

TSQM Version II

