10.6. Reporting of Serious Adverse Events

Any AE that meets the any criterion for a SAE requires the completion of an SAE Report Form in addition to being recorded on the AE pages of the CRF. The Sponsor Investigator(s) is required to ensure that the data on these forms is accurate and consistent. This applies to all SAEs, regardless of relationship to study drug, that occur during the study, those made known to the Sponsor Investigator(s) within 30 days after a subject's last dose of study drug, and those made known to the Sponsor investigator(s) at any time that are suspected of being related to study drug.

The SAE will be reported to the manufacturer of Clobetasol spray.

The SAE must be reported immediately (i.e., within 24 hours of the Sponsor Investigators' knowledge of the event) to Celgene Safety by facsimile. A written report (prepared by the Sponsor Investigator(s) using an SAE Report Form or a 3500A Medwatch form is to be faxed to Safety (see below for contact information).

Celgene Drug Safety Contact Information:

Celgene Corporation
Global Drug Safety and Risk Management
[name]
[name]
[contact]
E-mail: [contact]

The SAE report should provide a detailed description of the SAE. If a subject has died and an autopsy has been performed, copies of the autopsy report and death certificate are to be sent to Celgene as soon as these become available. Any follow-up data will be detailed in a subsequent SAE Report Form or Medwatch form and sent to Celgene.

The Sponsor Investigator(s) is responsible for informing the Institutional Review Board/Ethics Committee (IRB/IEC) of the SAE and providing them with all relevant initial and follow-up information about the event. The Sponsor Investigator(s) must keep copies of all SAE information, including correspondence with Celgene and the IRB/IEC, on file. All SAEs that have not resolved upon discontinuation of the subject's participation in the study must be followed until either the event resolves completely, stabilizes/resolves with sequelae, or returns to baseline (if a baseline value is available).

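### For patients who complete the study, no contact is scheduled after Week 16, so the protocol's own 28-day and 30-day post-dose windows rest on volunteered reports

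*Combined protocol and SAP*

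**What the plan says.** **Length and schedule.** Section 3 states: "The study is designed as a 16-week study and consists of 8 visits as described in the table of events". Section 3.2 repeats "Study Duration- 16 weeks". In the Table of Events (Section 4) the visits are screening and Weeks 0, 2, 4, 6, 8, 12 and 16. No later visit, call or pregnancy test appears.

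**End of treatment.** The Protocol Summary (Study Treatments) has patients "stop clobetasol but continue apremilast for a total of 16 weeks". The footnote to the Table of Events reads "Discontinue clobetasol spray 0.05% at Week 6". The same table marks dispensing of investigational product at Week 16.

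**Safety windows.**
- Section 10.1: adverse events are recorded "from the time of signing the informed consent through the end of the designated follow-up period".
- Section 5, Contraception Education: contraception is required "for at least 28 days after administration of the last dose of the investigational product".
- Section 10.6: the SAE rules extend to "those made known to the Sponsor Investigator(s) within 30 days after" the last dose of study drug.
- Section 10.7: pregnancies up to 30 days after the last dose are immediately reportable.

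**Rebound.** Section 5 states: "Rebound is an AE and is defined as a severe and sudden worsening of disease that occurs after treatment has been discontinued". One of its criteria is a PASI of at least 125% of baseline. Flare or rebound and PASI are both assessed at every visit.

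**The concern.** Three of the protocol's own rules look beyond the last dose by about a month, and a fourth (Section 10.1) runs to an endpoint that is not given. For a patient who takes apremilast to Week 16, the schedule stops on the day these windows open. Nothing prompts the site to ask about a new SAE, a pregnancy or a worsening of psoriasis in that month. The last pregnancy test is at Week 16, so it cannot show a conception that follows and may not show a very recent one.

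Safety is a secondary objective, and flare or rebound is a named safety assessment. If the report states that no SAEs, pregnancies or rebounds occurred after apremilast, a reader could not tell absence of events from absence of enquiry.

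**Working it through.** The plan gives no figure of its own to reproduce here. The sample size of about 20 is a feasibility number and plays no part. The check is calendar arithmetic on the Table of Events, with baseline as Day 0.

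**Inputs.** Visits at Weeks 0, 2, 4, 6, 8, 12 and 16 (Section 4); apremilast for 16 weeks in total (Protocol Summary); clobetasol stopped at Week 6 (Section 4 footnote); windows of 28 days (Section 5) and 30 days (Sections 10.6 and 10.7).

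**Step 1. Last visit and planned last dose.** 16 × 7 = Day 112.

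**Step 2. Scheduled contacts inside each post-dose window.**

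| Window | Ends | Scheduled contacts after the last dose |
|---|---|---|
| Contraception, 28 days | 112 + 28 = Day 140 (Week 20.0) | 0 |
| SAE, 30 days | 112 + 30 = Day 142 (Week 20.3) | 0 |
| Pregnancy, 30 days | 112 + 30 = Day 142 (Week 20.3) | 0 |

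**Step 3. Share of the reporting period.** Counted from baseline, 30 / (112 + 30) = 30 / 142 = 21.1%. Counted from consent with the full 7 days of screening, 30 / (7 + 112 + 30) = 30 / 149 = 20.1%. This is a share of calendar time, not an estimate of missed events.

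**Step 4. Rebound, by drug.** After clobetasol stops at Week 6, the remaining visits are at 8 − 6 = 2, 12 − 6 = 6 and 16 − 6 = 10 weeks. That gives three assessments, each with PASI. After apremilast stops at Week 16, a completer has none.

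**Step 5. Sensitivity to the Week 16 dispensing mark.** If product were taken after Week 16, the last dose would move. The documents give no quantity. Assuming a further supply of 2 to 4 weeks (the range of intervals between dispensing visits), the 30-day limit would fall between (112 + 14 + 30) / 7 = Week 22.3 and (112 + 28 + 30) / 7 = Week 24.3. The unobserved period would then be longer.

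**The case against.** **Rebound is assessed.** A reader might infer that the trial cannot observe rebound at all, or that zero rebounds are guaranteed by design. The documents do not support either. Clobetasol is the only drug for which the protocol raises rebound (Protocol Summary, Study Treatments), and Weeks 8, 12 and 16 cover its withdrawal. Section 11 also allows a patient to stop the product without leaving the study, so an early stopper could be assessed off apremilast. What remains is that completers are not assessed after apremilast, and that Section 5 does not say which treatment's discontinuation triggers the definition. At Weeks 8 to 16 patients are normally off one study drug and on the other, so this matters.

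**The rules are passive.** The SAE rule covers events made known to the investigator, the 28-day rule instructs the patient, and known SAEs and pregnancies are followed to outcome (Sections 10.4, 10.6 and 10.7). A reader might infer that the schedule contradicts these rules, or that events in the window are certain to be missed. Neither follows: a passive rule can run without a visit, and spontaneous reports may arrive. But following known events does not find new ones.

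**The follow-up period could mean the visits.** The Protocol Summary (Overview of Safety Assessments) refers to the visits at Weeks 2 to 16 as follow-up, so Section 10.1 can be read as ending at Week 16. That is a fair reading, but the protocol does not say so, and it would leave the post-dose month outside general AE recording.

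**Scale.** This is an open-label, descriptive pilot of 20 patients, and PASI 75 at Week 16 is untouched. That stands, and it sets the weight of the point.

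**Conclusion.** The point holds in a limited form. For completers, up to 20 of 20, the contraception, SAE and pregnancy windows contain no scheduled contact, and the endpoint of AE recording in Section 10.1 is undefined. About one fifth of the protocol's own reporting period (20.1% to 21.1%) therefore depends on volunteered reports, and worsening after apremilast is not assessed in these patients. The consequence is incomplete safety ascertainment, not a biased efficacy result.

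This rests on the last dose being taken at Week 16, as the Protocol Summary implies. The dispensing mark at Week 16 conflicts with that, and the two passages must be reconciled. Until they are, the end of the windows is not fixed. The documents give no basis for estimating how many events would be missed.

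The change is a cheap improvement that should be made; the trial's main conclusion does not depend on it.

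**What to change.** 1. **Table of Events (Section 4).** Add one telephone contact no earlier than 30 days after the last dose of study drug, for example day 30 to 37 (Day 142 to 149 if the last dose is on Day 112). Ask about AEs, SAEs, worsening of psoriasis and pregnancy. The window should not open before day 30: a call at 30 ± 3 days could fall on day 27, before either window closes. Adjust Sections 3 and 3.2 to match.
2. **Section 10.1.** Define the follow-up period, for example: *adverse events are recorded from consent until the follow-up telephone contact, made 30 to 37 days after the last dose of study drug.*
3. **Section 5.** State which treatment's discontinuation the rebound definition refers to.
4. **Week 16 dispensing.** Reconcile the mark in the Table of Events with the 16-week total in the Protocol Summary, since the timing of the call depends on it.
5. **Report.** State that worsening after apremilast was ascertained by telephone, to about 30 days only.

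**Cost.** About 20 calls, and an amendment with the approvals that Section 12.5 requires. Participation ends about 4 to 5 weeks later (30 / 7 = 4.3; 37 / 7 = 5.3).

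**What it does not solve.** A call cannot apply the PASI criterion for rebound. Without a test, it will not reliably detect a conception late in the window.
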